### 12.3 Rationale for Sample Size and Statistical Power

Sample size was established via simulation in R version 4.2.3 (R Core Team, 2023) utilizing preliminary data from clinics participating in a pilot study. This analysis is based on a within clinics, repeated measures design with two levels of EIMG exposure: Instructional Video and Onboard Training. The outcomes (e.g., referral rates) will be measured 4 times (once per month) under each level of EIMG, for a total of 8 observations per outcome per clinic. Two marginal referral rate profiles were considered in determining the sample size: a step effect of

EIMG onboarding with parallel time effect (main effects model) and a step plus accelerated time effect. A generic plot showing the two marginal rate profiles considered is presented in Figure 5.

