The subscripts i, j and k refer to clinic, EIMG status and time (monthly), respectively.  $Y_{ijk}$  is the clinic level outcome measure;  $g(Y_{ijk})$  is the link function;  $\beta_0$  is the mean response across clinics;  $\beta_1$  is the effect of EIMG;  $\beta_2$  is the mean effect of clinic level covariates controlling for EIMG status;  $\beta_3$  is the effect of time;  $\beta_4$  is the effect of the interaction between EIMG status and time. The remaining terms in the model represent random variability and are assumed to have an expected value of 0 and associated non-zero variance. Specifically,  $\mu_{0i}$  is the uncertainty term for the intercepts between clusters;  $\mu_{2i}$  is the uncertainty term for clinic level covariate slopes between clusters;  $\mu_{3k}$  is the uncertainty term for the effect of time;  $\mu_{4ijk}$  is the uncertainty term for EIMG by time interaction between clusters; and  $e_{ijk}$  is the unexplained residual.

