**Figure 5. Referral rate profiles considered in sample size analysis.**

Pilot data from 12 previously onboarded EIMG-clinics indicate the marginal referral rate (reach with eligible patients) prior to onboarding to EIMG is approximately 0.01. The following assumptions were made for both referral rate profiles. The standard deviation for the random effect of clinic, and random deviation is 0.01, the significance level for each comparison is 0.05. For the step with constant time effect, it was assumed that there was a linear change from 0.001 to 0.01 over the four months following the EIMG Instructional Video, a step-jump of 0.02, followed by a linear and parallel time effect achieving 0.04 (4%) referral rate at 8 months. For the step with accelerated time effect profile, the profile for the first 4 months was assumed to be the same as for EIMG Instructional Video with a step-jump of 0.01 followed by a linear increase to 0.04. Simulations (n=100) under each profile were conducted to compute a single empirical power, this was repeated 100 times. The power reported corresponds to the minimum empirical power observed. For a step with constant time effect a total of 10 clinics are needed to achieve a power of 92% to detect the EIMG Onboarding effect of 0.02. For the step plus accelerated time effect profile, a total of 20 clinics achieves 78% power to detect the time by EIMG status interaction when using a significance level of 0.05. Ten clinics provide 40% power to detect the step plus accelerated time effect profile.

#### 12.4 Secondary Aim 1

**To assess the effectiveness of participating in the community-based, 12-week evidence-informed PA program on EIMG-referred patient health outcomes (i.e., body weight, blood pressure, hemoglobin A1c, lipid profiles).**

*Hypothesis 1: Patients participating in the 12-week evidence-informed, community-based PA program will experience increased PA levels that is associated with a dose-response, significant reduction in body weight, systolic and diastolic blood pressure, hemoglobin A1c level, as well as improvements in their lipid profiles.*

Effectiveness is the degree to which participating in the evidence-informed PA programs improves patient physical activity levels and health outcomes (i.e., changes in cardiometabolic biometric values). Primary data for assessing effectiveness will be extracted from the Prisma

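### Section 12.3 powers two different tests of onboard training at 0.05 each and section 12.2 names neither as primary; if either result counts, the false-positive chance is about 7% to nearly 10%

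*Combined protocol and SAP*

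**What the plan says.** The Synopsis and section 6.2.1 give one primary outcome, the referral rate of eligible patients. Section 12.3 describes a within-clinic comparison of two exposure levels, Instructional Video and Onboard Training, with four monthly measurements under each, "for a total of 8 observations per outcome per clinic".

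For planning, "Two marginal referral rate profiles were considered in determining the sample size": a step with a parallel time trend, which the section ties to a main-effects model, and a step followed by a steeper trend. The assumptions listed for both include "the significance level for each comparison is 0.05" and "The standard deviation for the random effect of clinic, and random deviation is 0.01". The results are that "a total of 10 clinics are needed to achieve a power of 92% to detect the EIMG Onboarding effect of 0.02", that "a total of 20 clinics achieves 78% power to detect the time by EIMG status interaction when using a significance level of 0.05", and that "Ten clinics provide 40% power to detect the step plus accelerated time effect profile".

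Section 12.2 writes one GLMM with an EIMG term (β1), monthly time (β3) and their product. Of β4 it says that it "is the effect of the interaction between EIMG status and time". No origin is given for time. The documents state no primary contrast, no testing order, no alpha split and no overall type I error.

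**The concern.** The step and the interaction are different parameters, and each has its own test, power and number of clinics. Both p-values will exist once the 12.2 model is fitted. With nothing naming the one that decides, a study in which training did nothing could report either an immediate jump or a changed slope as the training effect. The 0.05 in 12.3 would then not be the error rate of that conclusion.

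The gap also affects power. In a model containing the product term, β1 is the difference between phases at time zero. Its meaning and precision therefore depend on how the months are coded, which the plan leaves open.

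**Working it through.** **Inputs** (section 12.3): clinic SD 0.01, residual SD 0.01, eight monthly rates per clinic, 0.05 per comparison, 10 or 20 clinics. Rates run from 0.001 to 0.01 in the first four months. They then go from a step of 0.02 to 0.04 (step profile), or from a step of 0.01 to 0.04 (accelerated profile). **Assumed:** two-sided tests, normal rates on the identity scale, random intercept only, EIMG status meaning training versus video. The timing of the profiles is a reading, because Figure 5 is not shown.

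**1. The plan's own powers.** Section 12.3 reports the minimum of 100 empirical powers, each from 100 simulations. With 0.001 at month 0, 0.01 at month 4 and the post-training line starting at month 5:

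| Test | Stated | One simulated minimum | Expected minimum |
|---|---|---|---|
| Step, 10 clinics | 92% | 91% | 90% |
| Interaction, 20 clinics | 78% | 78% | 78% |
| Interaction, 10 clinics | 40% | 43% | about 46% |

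The first two are reproduced closely, the third less well. With 0.001 at month 1 the fit is worse: minima of 89% for the step at 10 clinics and 61% for the interaction at 20.

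**2. Correlation of the two estimates.** Least-squares weights on months 1 to 8 are:
- step, main-effects model: 0.35, −0.05, −0.45, −0.85, 0.85, 0.45, 0.05, −0.35 (squares sum to 2.1)
- interaction: 0.3, 0.1, −0.1, −0.3, −0.3, −0.1, 0.1, 0.3 (squares sum to 0.4)

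The product-sum is 0.105 − 0.005 + 0.045 + 0.255 − 0.255 − 0.045 + 0.005 − 0.105 = 0, so the estimates are uncorrelated here.

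With uncentred months, β1 equals the level difference at month 4.5 minus 4.5 × β4:
- variance factor: 2.1 + 4.5² × 0.4 = 10.2
- covariance with β4: −4.5 × 0.4 = −1.8
- correlation: −1.8 / √(10.2 × 0.4) = −0.89

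**3. False-positive chance if either test counts.** For independent tests it is 1 − 0.95² = 9.75%. Null simulation with a time trend but no training effect (100,000 trials each) gives:

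| How the step is obtained | 10 clinics | 20 clinics |
|---|---|---|
| Main-effects model | 9.8% | 9.6% |
| β1, time centred at 4.5 | 9.8% | 9.6% |
| β1, origin at month 1 | 7.4% | 7.5% |
| β1, months 1–8 uncentred | 7.0% | 7.2% |

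**4. Effect of time coding on power.** For the step profile (0.001 at month 1), β1 from the written model has 95% power at 10 clinics if time is centred at 4.5, but about 32% with uncentred months. At 20 clinics the figures are above 99% and about 57%.

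**5. The joint 2-df test** of β1 = β4 = 0 does not change with the time origin. Its null rejection rate was 4.8–5.2%. Ordinary power, not the minimum of 100, is:

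| Profile, clinics | 0.001 placed at | Single test | Joint test |
|---|---|---|---|
| Step, 10 | month 1 | 95% | 90–91% |
| Step, 10 | month 0 | 95.8% | 92.5% |
| Step, 20 | month 1 | >99% | >99% |
| Accelerated, 20 | month 1 | 72–74% | 77–78% |
| Accelerated, 20 | month 0 | 87.4% | 89.4% |

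The single test is the main-effects step in the step rows and the interaction in the accelerated rows.

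**The case against.** The best reply is that the two profiles are alternative assumptions about the truth, used only to choose a number of clinics. The 0.05 per comparison stands among the simulation assumptions, and section 12.2 gives one model form for one outcome. A reader might infer from 12.3 that the study will run two co-primary tests, either of which suffices, and that its error rate is therefore 10%. The documents do not say that. If one coefficient is meant to be primary, the error is 5%. This part of the reply stands, and it makes the inflation conditional.

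Three further limits also stand:
- Nearly 10% needs a main-effects step or centred time. The written model with uncentred months gives about 7%.
- The zero correlation belongs to the simple set-up of 12.3. Section 12.2 adds random time and EIMG-by-time terms and allows other links. With rates between 0.001 and 0.04 on a logit scale, information differs by month and the balance argument does not carry over automatically.
- The joint test is not the only valid remedy, and its power gains depend on the profile timing.

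None of this supplies the missing rule. The two profiles are powered on different hypotheses, and nothing says which one decides.

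**Conclusion.** The point holds as an unspecified primary test, not as a demonstrated 10% error rate. The plan powers the step and the interaction at 0.05 each and fits both, without saying which supports a claim that training changed referral. If either would count, the false-positive chance is about 7% to nearly 10%, depending on where the step is read. This rests on two-sided tests, normal monthly rates, random intercepts only and the identity scale. It has not been shown for the fuller random-effects model or other links in 12.2.

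The power consequence does not depend on the either-counts condition. If β1 were read as the training effect with uncentred months, power for the step profile at 10 clinics would be about 32%, against the 92% stated.

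**What to change.** In 12.2, state one primary test of onboard training at 0.05. The preferred choice is the joint 2-df test that the EIMG and EIMG-by-time coefficients are both zero. Report the step and the slope change with confidence intervals as description of that result, and state the time origin at which the step is read. In 12.3, restate the power for that test under both profiles.

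**Cost.** SAP wording, one extra contrast and a rerun of the power simulation, with no added clinics or data. Power falls by about 3–5 points for a pure step at 10 clinics and rises by about 2–4 points for the accelerated profile at 20, depending on profile timing. The joint test is non-directional, so direction must be read from the estimates.

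**Alternatives that also hold 5%.**
- One named primary contrast with a stated time origin.
- A fixed sequence (simulated 4.9–5.1%). Testing the step first would usually block the interaction under the accelerated profile, because the step test then has only about 33–34% power at 20 clinics (0.001 at month 1).
- Splitting alpha at 0.025 each (simulated 4.9–5.0%). With 0.001 at month 1, this leaves about 92% power for the step at 10 clinics and 63% for the interaction at 20.

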**Figure 5. Referral rate profiles considered in sample size analysis.**

Pilot data from 12 previously onboarded EIMG-clinics indicate the marginal referral rate (reach with eligible patients) prior to onboarding to EIMG is approximately 0.01. The following assumptions were made for both referral rate profiles. The standard deviation for the random effect of clinic, and random deviation is 0.01, the significance level for each comparison is 0.05. For the step with constant time effect, it was assumed that there was a linear change from 0.001 to 0.01 over the four months following the EIMG Instructional Video, a step-jump of 0.02, followed by a linear and parallel time effect achieving 0.04 (4%) referral rate at 8 months. For the step with accelerated time effect profile, the profile for the first 4 months was assumed to be the same as for EIMG Instructional Video with a step-jump of 0.01 followed by a linear increase to 0.04. Simulations (n=100) under each profile were conducted to compute a single empirical power, this was repeated 100 times. The power reported corresponds to the minimum empirical power observed. For a step with constant time effect a total of 10 clinics are needed to achieve a power of 92% to detect the EIMG Onboarding effect of 0.02. For the step plus accelerated time effect profile, a total of 20 clinics achieves 78% power to detect the time by EIMG status interaction when using a significance level of 0.05. Ten clinics provide 40% power to detect the step plus accelerated time effect profile.

#### 12.4 Secondary Aim 1

**To assess the effectiveness of participating in the community-based, 12-week evidence-informed PA program on EIMG-referred patient health outcomes (i.e., body weight, blood pressure, hemoglobin A1c, lipid profiles).**

*Hypothesis 1: Patients participating in the 12-week evidence-informed, community-based PA program will experience increased PA levels that is associated with a dose-response, significant reduction in body weight, systolic and diastolic blood pressure, hemoglobin A1c level, as well as improvements in their lipid profiles.*

Effectiveness is the degree to which participating in the evidence-informed PA programs improves patient physical activity levels and health outcomes (i.e., changes in cardiometabolic biometric values). Primary data for assessing effectiveness will be extracted from the Prisma

Health EHR to allow comparisons between patients that are engaged in EIMG and participate in the evidence-informed PA programs and patients that do not participate (either those that are not engaged in EIMG by their providers or those who choose not to participate). Disease incidence, burden, and complications (i.e., the Charlson Comorbidity Index) may also be calculated from data captured in the EHR. Secondary assessment of patient-level effectiveness (e.g., blood pressure, blood glucose, cholesterol concentrations) will be collected by the EIMG Ex Pros at the community PA facilities.

Qualitative Data Collection. As part of our mixed methods approach, we will conduct semi-structured individual interviews with patients from each participating clinic. Patients will be randomly selected from one of three categories:

- i. Patients who received a referral from their provider, *but chose not to enroll in the evidence-informed PA program*, will be queried about their awareness of and reasons for not enrolling (i.e., perceived challenges to participation)
- ii. Patients who received a referral and enrolled, *but dropped out of the evidence-informed PA program*, will be asked about their perceptions of and satisfaction with the program, motivations for enrolling, and reasons for discontinuation, and
- iii. Patients who *enroll and complete the program* will be queried about their motivations for enrolling, perceptions of and satisfaction with the program, and challenges encountered.

Analysis of Qualitative Data. [name] will oversee the collection and analysis of the patient interviews. We will employ a rigorous approach to the analysis of the qualitative data. Open-ended responses will be uploaded to a qualitative software program (e.g., Dedoose) to create and apply codes to textual data, write analytic memos, and conduct analyses by question and respondent. Individual responses will be analyzed as follows: responses will be reviewed to develop an initial coding scheme for each question. Codes will be developed deductively from the questions posed and inductively from responses. As new codes emerge, they will be incorporated into the schemes for each question. A coding manual with definitions for each code will ensure high levels of intercoder reliability (>80%) are achieved throughout the coding process. Disagreements in the application of codes will be resolved by Drs. [name] and/or [name]. The analyses will catalogue facilitators, barriers, and challenges to EIMG® implementation in each phase, as well as strategies for overcoming those barriers.

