This multiple case study design will examine the adoption, implementation, and reach of EIMG (i.e., clinic workflow, referral process) across Prisma Health primary care clinics. Twenty Prisma Health primary care clinics will have the opportunity to adopt EIMG beginning in August 2023. Adopting clinics will receive a standardized instructional video and have the EIMG referral process activated, allowing providers to refer eligible patients to the 12-week evidence-informed PA program. In January 2024, adopting clinics will receive an in-depth, tailored EIMG onboard training. At EIMG adopting clinics, we will track referral rates of eligible patients over two phases lasting a total of eight months (months 1-4 after instructional video, months 5-8 after tailored onboard training).

We will use a mixed methods approach to explore factors related to the adoption of EIMG (i.e., characteristics of adopting versus non-adopting clinics), achieving optimal implementation (i.e., clinic workflow, referral process), reach (i.e., proportion of eligible patients receiving a referral, characteristics of referred versus non-referred patients), and patient enrollment in evidence-informed PA programs at participating community PA facilities. The RE-AIM framework will inform the assessment of implementation outcomes, while the i-PARIHS framework will be used to understand contextual factors (i.e., determinants) influencing patient- and clinic-level outcomes. Careful attention will be paid to issues of health equity across all RE-AIM dimensions over the course of the study. Finally, this work will examine the impacts of EIMG implementation on healthcare costs and patient outcomes to assess the cost-effectiveness associated with implementing EIMG in a major health system.

Integrating the EIM model in health systems to connect patients with available community resources has the potential to significantly alter clinical practice and improve population health outcomes. Information gained from this study will lead to the development of a generalizable approach and materials that will inform future implementation strategies on optimizing and scaling up the integration of comprehensive PA models in U.S. health systems. Study findings will also provide cost estimates of potential savings to health systems integrating PA as a population health management tool through clinic-community linkages.

Figure 1. Overall study schematic.

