### **6.2.7 Rationale for Control Condition**

The selection of our control group was influenced by several factors. There are currently only 20 Prisma Health primary care clinics that have not received EIMG onboarding and activation and that are within 15 miles or less of a participating community PA facility. There are no other equivalent Prisma Health primary care clinics to serve as matched controls (i.e., via a stepped wedge design). We are then left with two groups of clinics to serve as controls. The first of these is using a within-clinic design and comparing patient health outcomes before and after the dissemination of the initial EIMG Instructional Video. Secondly, from past experiences, we anticipate that several of the 20 clinics will choose not to adopt EIMG and/or will be non-responsive to our invitation. As one of our study aims, we will evaluate contextual factors and differences between adopting and non-adopting clinics. Clinics that do not adopt EIMG will not be 'activated' and can therefore serve as control clinics, particularly when evaluating patient-level outcomes, as none of their patients will have had the opportunity to participate in EIMG.

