## **8.0 STUDY PROCEDURES**

### **8.1 Waves of Enrollment**

All eligible Prisma Health primary care clinics will be invited to adopt EIMG at the same time. Prisma Health primary care clinics will not enter clinics into the study via stepped approach. Within this one wave, three distinct study phases will be conducted.

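### Section 12.3 states 78% interaction power at 20 clinics, the whole eligible pool, although several are expected not to adopt; and 12.2 gives no time origin, so its EIMG coefficient is undefined

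*Combined protocol and SAP*

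**What the plan says.** Section 12.3 bases the sample size on a within-clinic comparison of two exposure levels, Instructional Video and Onboard Training, with four monthly values under each. Two true profiles are assumed: a step with parallel slopes, labelled a main-effects model, and a step with a steeper slope afterwards.

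- Step: "a total of 10 clinics are needed to achieve a power of 92% to detect the EIMG Onboarding effect of 0.02".
- Interaction: "For the step plus accelerated time effect profile, a total of 20 clinics achieves 78% power to detect the time by EIMG status interaction", and "Ten clinics provide 40% power to detect the step plus accelerated time effect profile".
- How power is reported: each empirical power comes from 100 simulations, this is repeated 100 times, and "The power reported corresponds to the minimum empirical power observed".
- Variability: "The standard deviation for the random effect of clinic, and random deviation is 0.01". No other standard deviation is given.

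On the number of clinics, section 6.2.7 says that only 20 clinics are eligible and that "we anticipate that several of the 20 clinics will choose not to adopt EIMG and/or will be non-responsive to our invitation". Section 8.1 adds: "All eligible Prisma Health primary care clinics will be invited to adopt EIMG at the same time". The synopsis (2.0) restricts tracking: "At EIMG adopting clinics, we will track referral rates of eligible patients over two phases lasting a total of eight months".

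Section 12.2 gives one model whose right-hand side keeps the same form for every outcome. It contains EIMG status (beta_1), time (beta_3) and their interaction (beta_4), with random terms for time and for the interaction. It describes beta_1 as the effect of EIMG. It states neither where time is zero nor which coefficient is the primary test.

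**The concern.** There are two separate issues.

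**Number of clinics.** The favourable interaction figure is quoted at the ceiling of the available pool. Non-adopters are not activated, so they have no video or onboarding months and add nothing to a within-clinic contrast. With a single invitation wave there is no reserve to replace them. The plan gives no expected number of adopters and no power between 10 and 20 clinics, which is where the trial is likely to fall. If 12 to 16 clinics adopt, a non-significant interaction could be read as evidence that training does not accelerate referral, although the design had limited ability to show it.

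**Time origin.** With beta_4 in the model, beta_1 is the video-to-onboarding difference at T = 0. If T = 0 lies before month 1, that is an extrapolation well away from the changeover. Both the value and the precision of beta_1 then depend on a coding choice that the plan does not state, while its label invites a reader to take it as the training effect.

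**Working it through.** **Inputs.** From 12.3: 8 monthly values per clinic (4 + 4); clinic and residual SD 0.01; significance level 0.05 (sidedness not stated, two-sided assumed). Video phase: 0.001 to 0.01 over four months. Accelerated profile: 0.02 rising to 0.04. Step profile: jump of 0.02, so month 5 at 0.03. Assumed here: adopter counts of 12 to 18, because the plan gives none.

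**Formulas** (random clinic intercept, sigma = 0.01, n clinics). Within each phase the squared deviations of the four months sum to 5.

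- Var(beta_4) = 2 × sigma²/(5n) = 0.4 sigma²/n, for any time origin.
- Var(step, no interaction in model) = 2.1 sigma²/n.
- Var(beta_1, interaction in model, origin t0) = (sigma²/n) × [0.5 + ((2.5 − t0)² + (6.5 − t0)²)/5].
- Power from the noncentral t, with 7n − 3 degrees of freedom (7n − 2 without the interaction).
- Expected minimum of 100 batches of 100 = (1/100) × sum over k = 1 to 100 of P(X ≥ k)^100, where X ~ Binomial(100, power).

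**Reproducing the stated figures.** Take the video slope as 0.009/4 = 0.00225 per month.

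- Step: month 5 extrapolated from the video phase is 0.01 + 0.00225 = 0.01225, so the net step is 0.03 − 0.01225 = 0.01775. At n = 10 the SE is 0.00458, power 96.8%, expected minimum 91.7% (stated 92%).
- Interaction: 0.02/3 − 0.00225 = 0.00442 per month. At n = 20 the SE is 0.00141, power 87.3%, expected minimum 78.4% (stated 78%).
- Interaction at n = 10: SE 0.0020, power 58.6%, expected minimum 46.1% (stated 40%, not reproduced).

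**Interaction power by number of adopters, same reading.**

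| Adopters | Expected power | Expected minimum |
|---|---|---|
| 10 | 59% | 46% |
| 12 | 67% | 55% |
| 14 | 74% | 62% |
| 16 | 79% | 68% |
| 17 | 82% | 71% |
| 18 | 84% | 74% |
| 20 | 87% | 78% |

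**Time origin, 10 clinics, interaction in the model, net step 0.017 to 0.020.**

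| Coding of T | Variance factor | SE(beta_1) | Power of beta_1 |
|---|---|---|---|
| Months 1-8 (t0 = 0) | 0.5 + (6.25 + 42.25)/5 = 10.2 | 0.0101 | 38-50% |
| Centred at 4.5 | 0.5 + (4 + 4)/5 = 2.1 | 0.0046 | 95-99% |

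**Sign of beta_1 under the accelerated profile (identity scale).** With months coded 1-8, the onboarding line at T = 0 is 0.02 − 5 × 0.00667 = −0.0133. If the video phase starts at 0.001 in month 1 and rises 0.003 per month, its line at T = 0 is −0.002, so beta_1 = −0.0133 + 0.002 = −0.011. If it starts at 0.001 at month 0 and rises 0.00225 per month, beta_1 = −0.0133 − 0.001 = −0.014. Centred at 4.5, beta_1 is about +0.005 to +0.006. A beneficial training can therefore carry a negative beta_1 purely through coding.

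**The case against.** The strongest reply is that nothing in 12.3 has been shown to be miscalculated. The 78% and 92% both reproduce on a natural reading of the profiles. The figures are openly labelled as minima and so are conservative, and 40% at 10 clinics is disclosed. The loss of three or four clinics leaves expected power at 79-82%, about the number stated. All of that stands. A reader might infer that the 78% is wrong or that the plan hides the fall in power; the documents support neither.

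A reader might also infer that the 92% comes from fitting a main-effects model and is lost once beta_4 enters. The main-effects label in 12.3 describes an assumed profile, and the model fitted in the simulation is not stated. With time centred at 4.5, the variance factor with the interaction is 2.1, the same as without it, so the step loses essentially nothing. The 38-50% applies only under an uncentred coding that the plan does not specify, with beta_1 read alone as the test.

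The video slope could also be taken as 0.009 over three intervals (0.003 per month). That gives expected interaction power of only 51%, 57% and 63% at 12, 14 and 16 clinics, but an expected minimum of 62% at 20, which does not match the stated 78%. I do not rely on it. Figure 5, which is not visible in the text reviewed, may settle the reading.

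Finally, 12.2 leaves the link open, and an interaction depends on scale. No link is stated for the primary outcome, so this supports only a request about reporting scale, not a finding of error.

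**Conclusion.** The point holds as a reporting and specification gap in the primary-outcome analysis that should be fixed.

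The interaction power of 78% is a ceiling figure that the plan's own adoption forecast does not expect to reach. With 12 to 18 adopters, minimum-type power is about 55% to 74% and expected power about 67% to 84%, passing 80% at about 17. On expected power the design therefore tolerates about three non-adopters. These values rest on assumed adopter counts, two-sided testing, a random clinic intercept only, and the 0.00225 slope. On that reading the stated 40% at 10 clinics comes out at 46%, so the 40% and 78% still need reconciling.

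The random time and interaction terms in 12.2 have no stated SDs, and variation in the interaction slope would lower power further. As an illustration, with a clinic-level t test and an assumed interaction-slope SD of 0.002 to 0.006, power at 20 clinics falls from 84% to between 81% and 58%.

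The step is well powered provided time is centred near the changeover. Until the origin is fixed, beta_1 cannot be read as the training effect.

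**What to change.** In 12.3:
- Replace the single 20-clinic figure with interaction power across plausible adopter counts, for example 10 to 18, with 20 shown as the ceiling.
- Report mean empirical power alongside any minimum, each labelled as such.
- Reconcile the 40% and 78%, and give the monthly profile values used.
- Rerun the simulation with the 12.2 model, including beta_4 and its random time and interaction terms, and state the SDs assumed for them.

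In 12.2:
- Define EIMG for this analysis as video versus onboard training, with time centred at the switch.
- Name the primary contrast. The step is the better powered, but the choice is the sponsor's.
- State the link, and report the effect in percentage points, the scale that was powered, whichever link is used.

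The cost is a few hours of simulation and some SAP wording. The stated interaction power becomes less favourable. Recruitment and conduct are unaffected, because the clinic pool is fixed.
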